1.8.7 Benefit/Risk Conclusion

This study is primarily a patient safety and tolerability study to inform further clinical development, and whilst those asthma patients who receive UPB-101 could derive benefit, this is not the main objective of the study. Subjects will continue to administer their usual stable, non-biologic asthma medication regimen during participation in the study.

The risks of participation are mainly those associated with possible side effects to UPB-101, although there may also be some discomfort from collection of blood samples and other study procedures. The study will be conducted at Medicines and Healthcare products Regulatory Agency (MHRA)-accredited Phase 1 facilities and procedures/interventions will be performed by qualified and trained professionals. Subjects will undergo Coronavirus disease 2019 (COVID-19) testing as per each site's protocol.

One previous human clinical study has been completed with UPB-101, in healthy volunteers, and in this study single increasing doses from █ mg/kg body weight administered intravenously, or █ mg/kg body weight administered subcutaneously, were considered safe

and well-tolerated. As detailed above, the Sponsor has identified risk minimization actions based upon non-clinical toxicology studies with UPB-101.

The Sponsor believes that the potential risks to subjects are proportionate for the proposed study, and that these will be addressed through risk minimization activities and through the conduct of the study at three sites with significant Phase 1 asthma clinical trial experience.

2 STUDY OBJECTIVES AND ENDPOINTS

Primary Objective

The primary objective in this study is the assessment of the safety and tolerability of UPB-101 when administered as multiple ascending doses.

Primary Endpoints

The primary endpoints are AEs, SAEs, physical examinations, clinical laboratory assessments, vital signs, and electrocardiograms (ECGs). Subject withdrawals, early terminations, and dosing compliance are also assessed. Data collected from baseline through Week 24 are included. These endpoints are evaluated in the Safety Population (defined in Section 9.3).

Secondary Objectives

The secondary objectives are the assessment of the immunogenicity and PK of multiple ascending doses of UPB-101.

Secondary Endpoints

The secondary endpoints include UPB-101 anti-drug antibodies (ADAs) and serum UPB-101 concentrations and analyses including C_{max} , t_{max} , AUC_{tau} . If appropriate, AUC_{inf} , $t_{1/2}$, apparent total body clearance after dosing (CL/F), and apparent volume of distribution during the terminal elimination phase after dosing (V_z/F), all after the first dose, will be analysed as well. These endpoints are assessed from baseline through Week 24 in the PK Population (defined in Section 9.3).

Exploratory Objectives

The exploratory objectives in this study include the assessments of the:

1. Extended 32-week safety and tolerability of UPB-101 when administered in multiple ascending doses.
2. Extended 32-week immunogenicity and PK of UPB-101 when administered in multiple ascending doses.
3. Pharmacodynamic effect of UPB-101 on biomarkers related to asthma and/or TSLP-related biomarkers.
4. Pharmacodynamic effect of UPB-101 on clinician and subject impressions of overall asthma activity.
5. Pharmacodynamic effect of UPB-101 on lung function

Exploratory Endpoints

The exploratory endpoints include:

1. AEs, SAEs, pregnancy tests, and changes from baseline in physical examinations, clinical laboratory assessments, vital signs, and ECGs. Subject withdrawals, early termination, and dosing compliance are also assessed. Data collected from baseline through Week 32 are included. These endpoints are evaluated in the Safety Population (defined in Section 9.3).
2. UPB-101 ADAs, presence of neutralizing antibodies (NAb) and serum UPB-101 concentrations and analyses including C_{max} , t_{max} , AUC_{tau} . Data collected from baseline through Week 32 in the PK Population (defined in Section 9.3) are included.
3. FeNO and blood eosinophil numbers from baseline through Weeks 24 and 32. Total IgE; IL-5, IL-13, IL-17A, interferon gamma (IFN λ), IFN λ -induced protein 10 (IP-10), TSLP, eotaxin-3, tryptase, carboxypeptidase, thymus activation regulated chemokine (TARC), C-reactive protein (CRP) concentrations; and flow cytometric assessments of phosphorylated signal transducer and activator of transcription (pSTAT) and receptor occupancy will be evaluated from baseline through Weeks 24 and 32. These PD markers are evaluated in the PD Population (defined in Section 9.3).
4. Clinician Global Impression of Change (CGI-C) and Subject Asthma Control Questionnaire (ACQ-7) from baseline through Weeks 24 and 32. These PD markers are evaluated in the PD Population (defined in Section 9.3).
5. Forced expiratory volume in 1 second (FEV_1) from baseline through Weeks 24 and 32. These PD markers are evaluated in the PD Population (defined in Section 9.3).

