These data provide the rationale for the parallel cohort design. For all cohorts, the projected single dose exposures are lower than the exposures that were found to be safe and well tolerated in Study 7266-CL-0001.

Table 1 Predicted Mean PK parameters After Single SC Administration UPB-101 Compared to the Maximal IV Dose of Completed Study 7266-CL-0001

Route	Single Dose				Fraction of Maximal SAD Exposure	
	Dose (mg)	Dose (mg/kg)	C_{max} ($\mu\text{g}/\text{mL}$)	AUC_{inf} (days· $\mu\text{g}/\text{mL}$)	C_{max} IV/ C_{max} SC	AUC_{inf} IV/ AUC_{inf} SC
SC	█	█	█	█	█	█
SC	█	█	█	█	█	█
SC	█	█	█	█	█	█
SC	█	█	█	█	█	█
IV	█	█	█	█		

AUC_{inf} =area under the concentration-time curve from the time of dosing extrapolated to time infinity; C_{max} =maximum observed concentration; IV=intravenous; PK=pharmacokinetic; SAD=single ascending dose; SC=subcutaneous.

Local Tolerability

All subjects enrolled in this study will receive █ mg or █ mg SC injections at each dosing visit depending upon to which cohort they are assigned. For example, subjects assigned to Cohort 1 (█ mg █) will received two █ mg SC injections at 2 separate injection sites at each dosing visit. The SC dose administered in the SAD study was █ mg/kg (█ mg) and was well-tolerated; no injection site reactions were reported. Therefore, no significant local skin reactions are anticipated in the current study.

Multiple Dose

[figure not shown]
The PK model described above was used to simulate multiple dose PK for the doses and dosing intervals to be administered in this study. Predicted PK parameters and predicted mean PK profiles after repeated SC administration of UPB-101 are shown in Table 2 and Figure 1, respectively. There is minimal accumulation after repeated administration, with close to steady state levels reached after 3 injection (for [REDACTED] regimen) or 2 injections (for [REDACTED] and [REDACTED] regimens). The predicted C_{max} and area under the concentration-time curve for one dosing interval (AUC_{tau}) in this study (at the highest dose of [REDACTED] mg SC) are [REDACTED]-fold and [REDACTED]-fold lower, respectively, when compared with the observed C_{max} and AUC_{inf} following administration of [REDACTED] mg/kg IV in Study 7266-CL-0001, a dose that was found to be safe and well- tolerated.

Table 2 Predicted Serum PK Parameters After Repeated SC Administration of UPB-101

Dose	Frequency	Number of doses	Multiple SC dose		
			Interval	C_{max} (µg/mL)	AUC_{tau} (days·µg/mL)

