
	Dosing Period					
	4	5	6	7	8	9
Visit	W0	W0	W0	W1	W2	W3
Study Week						
Procedures	D1	D2	D4	D8	D15	D22
Study Day						
Visit window (days)	0	0	0	±1	±2	±2
Pregnancy test ^a	X	X	X	X	X	X
Physical examination (symptom-driven)	X ^b					
Vital signs ^c	X		X		X	X
12-lead ECG ^d	X		X	X	X	X
Haematology & eosinophils ^f	X	X ^m	X ^m	X	X	
Blood chemistry ^g	X				X	
Urinalysis	X				X	
FeNO	X	X ⁿ	X ⁿ	X	X	
Pulmonary Function Tests (Spirometry) ^e	X			X	X	
Total IgE	X				X	
C-reactive protein	X				X	
Biomarkers ^j	X				X	
Future analysis of additional cytokines	X				X	
Flow cytometry ^l	X				X	
CGI-C and ACQ-7 ^h					X	
Serum for PK ⁱ	X	X	X	X	X	X
Serum ADA and NAb (immunogenicity)	X					
Randomization	X					
UBP-101 administration/post-dose observation	X					
COVID-19 protocol as per site SOPs	X	X	X	X	X	X
Admission (Ad) or Discharge (Di) from site	Di					
Subject contact ^k	(X)		(X)		(X)	
Concomitant medication	X	X	X	X	X	X
Assess injection site reactions	X	X	X	X		
Review/Record AEs	X	X	X	X	X	X

Admission days are highlighted in light gray and dosing days in dark gray.

Table 6 Schedule of Events - Cohorts with █ Dosing Interval

Visit	Dosing Period					Observation Period										
	10	11	12	13	14	15	16	17	18	19	20	21	22	23	24	25
Study Week	W3	W4	W5	W7	W8	W8	W8	W9	W10	W11	W12	W16	W20	W24	W28	W32
Procedures																D225/ Final Visit
Study Day	D28	D29	D36	D56	D57	D58	D60	D64	D71	D78	D85	D113	D141	D169	D197	
Visit window (days)	±2	±2	±1	±2	±2	0	0	±1	±2	±3	±3	±5	±5	±5	±5	±5
Pregnancy test ^a	X	X	X	X	X	X	X	X	X	X	X	X	X	X	X	X
Physical examination (full)																X
Physical examination (symptom-driven)	X ^b	X ^b	X ^b	X ^b	X ^b	X ^b	X ^b	X ^b	X ^b	X ^b						
Body weight																X
Vital signs ^c	X	X	X	X	X	X	X	X	X	X	X	X	X	X	X	X
12-lead ECG ^d		X	X		X		X	X	X		X	X	X			X
Haematology & eosinophils ^f		X	X		X				X		X	X	X	X	X	X
Blood chemistry ^g		X	X		X				X		X	X	X			X
Urinalysis		X	X		X				X		X	X	X			X
Total IgE			X								X	X	X	X	X	X
C-reactive protein		X			X						X	X	X	X	X	X
FeNO		X			X						X	X	X	X	X	X
Pulmonary Function Tests (Spirometry) ^e		X			X						X	X	X	X	X	X
Biomarkers ^j		X			X						X	X	X	X	X	X
Future analysis of additional cytokines		X			X						X	X	X	X	X	X
Flow cytometry ^k		X			X						X	X	X	X	X	X
CGI-C and ACQ-7 ^h	X			X							X	X	X	X	X	X
Serum sample for PK ⁱ		X			X	X	X	X	X	X	X	X	X	X	X	X
Serum ADA and NAbs (immunogenicity)		X			X						X	X		X		X
Study drug administration		█			█											

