3.6.1 Cohorts with [REDACTED] Dosing Intervals

The Dosing Period of cohorts with [REDACTED] dosing intervals (e.g., Cohorts 1 and 2 in Part A) will last [REDACTED] weeks (Days [REDACTED]). Subjects assigned to this cohort will receive 3 doses of study drug at [REDACTED] intervals. The assessments to be conducted on subjects in these cohorts during the Dosing Period and their timing are listed in Table 5 and Table 6.

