5.6 Pharmacokinetic Assessments

Timed serum samples will be collected to determine the concentration of UPB-101 and will be collected as detailed in Table 4 through Table 9 in Section 3.3. Pharmacokinetic serum samples will be collected pre-dose on dosing days.

When the PK sampling coincides with the ECG and/or vital sign recordings, priority should be given to the ECGs and vital signs. The actual date and time of each PK sample collection will be recorded in the eCRF.

Blood sample collection, handling, and storage will be described in the laboratory manual.

The PK analyses will be based on the timed blood PK sampling of all enrolled subjects (PK Population). Serum UPB-101 concentrations will be summarized using descriptive statistics and used for PK analyses including the following endpoints if appropriate:

- C_{max} .
- t_{max} .
- AUC_{tau} .
- AUC_{inf} after the first dose, if appropriate.
- $t_{1/2}$, if appropriate.
- CL/F , if appropriate.
- V_z/F , if appropriate.

A power model will be fitted using all doses and across all cohorts to assess dose proportionality for C_{max} and AUC_{tau} after the first dose. Within each dosing regimen, dose proportionality using a comparison of C_{max} and AUC_{tau} after the last dose will also be assessed using descriptive statistics. For each dosing regimen, accumulation of UPB-101 will be assessed by comparing the ratio of C_{max} and AUC_{tau} after the last dose and the first dose for each subject and summarized by dosing regimen.

Analysis of UPB-101 will be performed using a validated method at a bioanalytical laboratory specified by the Sponsor.

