### 7.2. Secondary Endpoints

The secondary endpoints include UPB-101 anti-drug antibodies (ADAs) and serum UPB-101 concentrations and analyses including  $C_{max}$ ,  $t_{max}$ ,  $AUC_{tau}$ . If appropriate,  $AUC_{inf}$ ,  $t_{1/2}$ , apparent total body clearance after dosing (CL/F), and apparent volume of distribution during the terminal elimination phase after dosing (Vz/F), all after the first dose, will be analyzed as well. These endpoints are assessed from baseline through Week 24 in the PK Population.

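### In the 3-dose cohorts, half-life, CL/F and Vz/F are tied to a first-dose profile cut off at about 28 days, although the washout after the last dose is sampled far longer

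*Protocol*

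**What the plan says.** Protocol Section 2 (Secondary Endpoints) names Cmax, tmax and AUCtau. It then adds AUCinf, half-life, CL/F and Vz/F where appropriate, "all after the first dose, will be analysed as well". The synopsis has the same restriction, and SAP 7.2 repeats it: "all after the first dose, will be analyzed as well". These endpoints run to Week 24.

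The list in Protocol 5.6 is different. It gives "AUC_{inf} after the first dose, if appropriate" but attaches no dose to half-life, CL/F or Vz/F; the last entry reads only "V_z/F , if appropriate". The Week 32 exploratory PK endpoint in Section 2 names Cmax, tmax and AUCtau, so no endpoint there asks for a half-life from the washout.

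Protocol 3.6.1 covers the 3-dose cohorts, such as Cohorts 1 and 2: "Subjects assigned to this cohort will receive 3 doses of study drug at" a redacted interval. SAP 10.9 sends the PK specification to a separate PK analysis plan, which is not among the documents.

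**The concern.** Half-life, and Vz/F with it, depends on the terminal slope. CL/F after a single dose depends on AUCinf, and so on the same slope through extrapolation. In the 3-dose cohorts the second dose interrupts the first-dose decline, while the uninterrupted decline follows the third dose. Read literally, the endpoint text uses the short segment for these parameters and sets the long one aside.

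Two of the three Part A cohorts would then have imprecise values or, under the if-appropriate proviso, none. The same parameter would be well determined in Cohort 3 and, if it is run, Cohort 4, so comparisons across cohorts would mix very different reliability. Because Section 5.6 reads differently, two analysts could also follow the documents and report different quantities under one name.

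**Working it through.** **Inputs from the documents**
- Dosing days in the 3-dose cohorts: the interval is redacted. Days 1, 29 and 57 are inferred from the marked columns of the "Study drug administration" row in Protocol Table 6.
- PK samples after dose 1: Days 2, 4, 8, 15 and 22 (Table 5) and Day 29 (Table 6). Footnote i makes dosing-day samples pre-dose, so the profile ends at 29 − 1 = 28 days.
- PK samples after the last dose ("Serum sample for PK" row, Table 6): Days 58, 60, 64, 71, 78, 85, 113, 141, 169, 197 and 225. That is 169 − 57 = 112 days to Week 24 and 225 − 57 = 168 days to Week 32.
- First-dose window elsewhere: Cohort 3, 85 − 1 = 84 days; Cohort 4 (single dose), 225 − 1 = 224 days (Table 8).

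**Assumptions**
- Half-life (not given). Protocol 1.7 states "There is minimal accumulation after repeated administration, with close to steady state levels reached after 3 injection" for one redacted regimen, taken here to be the 3-dose one. If three 28-day intervals but not two reach a fraction f of steady state, the half-life lies between 56·ln2/(−ln(1−f)) and 84·ln2/(−ln(1−f)). That is 16.9 to 25.3 days for f = 0.90 and 13.0 to 19.4 days for f = 0.95. I use 14 to 25 days.
- One-compartment model with first-order absorption, absorption half-life 2 to 3 days.
- Residual CV 15%, constant on the log scale.

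**AUC beyond time T.** With k and ka the elimination and absorption rates, the fraction is (e^(−kT)/k − e^(−ka·T)/ka) / (1/k − 1/ka). For half-life 14 and absorption half-life 2 days, k = 0.0495 and ka = 0.3466. At T = 28 this gives about 5.05/17.31 = 0.29. For 25 and 3 days it gives about 16.59/31.74 = 0.52.

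**Slope precision.** The relative standard error of k is 0.15 / (k·√S), where S is the sum of squared deviations of the sampling times from their mean.
- Days 8, 15, 22, 29 (7, 14, 21, 28 days after dosing): S = 245.
- Days 71, 78, 85, 113, 141, 169 (14, 21, 28, 56, 84, 112 days after dosing): S = 7619.5.

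| Half-life (days) | Half-lives in D8–D29 | AUCinf beyond day 28 | Beyond day 84 (Cohort 3) | Slope SE, D8–D29 | Slope SE, D71–D169 |
|---|---|---|---|---|---|
| 14 | 1.50 | 29–32% | about 2% | 19.4% | 3.5% |
| 16.8 | 1.25 | 36–38% | about 4% | 23.2% | 4.2% |
| 21 | 1.00 | 44–46% | about 7% | 29.0% | 5.2% |
| 25 | 0.84 | 50–52% | about 11% | 34.6% | 6.2% |

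The ratio of the two standard errors is √(7619.5/245) = 5.6, whatever half-life and residual CV are assumed. If Day 169 is not quantifiable, Days 71 to 141 (S = 3371.2) give about 5% to 9%. If Day 8 is still in absorption or distribution, Days 15 to 29 (S = 98) give about 31% to 55%.

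In this model the extrapolated share at day 28 falls below 20% only if the half-life is under about 10 to 11 days.

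**The case against.** Much of the case on the other side stands, and it rules out stronger readings that a reader might infer.

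- *That the terminal phase is seen only after the last dose.* Not supported. Days 8 to 29 show a decline of about 0.8 to 1.5 half-lives under the assumed range. It is truncated, not unobserved.
- *That AUCinf is also misplaced.* It is not. After repeated dosing, an AUC from the last dose to infinity includes carry-over from earlier doses, so first-dose AUCinf is the right definition.
- *That the washout goes unused and Phase 2 intervals would rest on about one half-life.* Protocol 1.7 (Study Posology) says the Part A data, including the observation period after the final dose, will feed modelling of doses and intervals for Phase 2. Serum concentrations to Week 32 are also an exploratory endpoint.
- *That the upper half-life is likely.* At 25 days, AUCtau would accumulate 1/(1 − 0.52) = 2.1-fold, which fits poorly with the minimal accumulation stated in the same sentence. At 14 days it is 1/(1 − 0.29) = 1.4-fold. The lower part of the range is more credible, but the slope SE there is still 19% against 3.5%.

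The standard errors are per subject, and summaries average over six active subjects per cohort. The protocol's own model has two compartments, so these figures are indicative. These are optional descriptive parameters in a trial with no hypothesis test.

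Two defences do not succeed. The if-appropriate proviso governs whether a value is reported, not which dose it comes from. The PK analysis plan may name the last dose, but it would then contradict three endpoint statements, and it cannot be assumed to do so. Finally, SAP 10.8 reports a hold on dosing, so some first-dose windows may in practice be longer than 28 days.

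**Conclusion.** The point holds for half-life, CL/F and Vz/F in the 3-dose cohorts. Three endpoint statements confine them to a window of about 28 days, and Protocol 5.6 does not. For an assumed half-life of 14 to 25 days, the literal rule gives a per-subject slope SE of about 19% to 35%, where samples already scheduled within the Week 24 window give about 3.5% to 6%. It also leaves about 29% to 52% of AUCinf to extrapolation. The roughly 5.6-fold loss of precision depends only on the sampling days and log-linear decline with constant error. The absolute figures depend on the assumed half-life, absorption rate and 15% CV.

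Cohort 3, with an 84-day window and about 2% to 11% extrapolated, and Cohort 4, with a single dose, support first-dose terminal parameters. The conflict between Section 2 and Section 5.6 needs no half-life assumption at all. This should be corrected, but it does not threaten the primary objective.

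**What to change.** Align the synopsis, Protocol Section 2, Protocol 5.6, SAP 7.2 and the PK analysis plan as follows.

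- **Half-life:** estimate it from the terminal phase after the last dose received, in every cohort.
- **AUCinf:** keep it as a first-dose parameter. Report it, and any first-dose CL/F and Vz/F, only where the extrapolated fraction is below a stated limit, for example 20%.
- **CL/F in multiple-dose cohorts:** dose divided by AUCtau at the last dose, only for subjects who received all doses on schedule. The dosing hold makes that condition necessary.
- **Vz/F in multiple-dose cohorts:** that CL/F divided by the last-dose terminal slope, in the same subjects.
- **Stated limitation:** dose/AUCtau overstates CL/F if steady state is not reached. At 90% of steady state the bias is 1/0.90 − 1 = about 11% upward, and it carries into Vz/F.

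The cost is wording in the endpoint sections and the PK plan. Every sample needed is already scheduled.

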3 INVESTIGATIONAL PLAN

3.1 Overall Study Design and Plan

This is a 2-part Phase 1, randomized, double-blind (Investigator and Subject blinded; Sponsor unblinded), placebo-controlled, multiple ascending -dose study to assess the safety, tolerability, immunogenicity, PK, and PD of UPB-101 administered SC to approximately 40 subjects with asthma. The study is expected to last from June 2022 to October 2023.

3.1.1 Study Design: Cohorts

The study will be conducted in 3-5 sites in the United Kingdom.

The study consists of Part A and Part B. Part A includes 3 cohorts with pre-set dosing regimens. Part B includes up to 2 optional adaptive design cohorts whose doses and dosing intervals will be decided based upon the safety, PK, and PD results from Part A available to the unblinded Sponsor. The regimens selected for Part B will not exceed the exposures (i.e., doses and/or dosing intervals) included in Part A.

The study will consist of 3 to 5 cohorts: 3 cohorts in Part A and up to 2 optional cohorts in Part B. Eight subjects will be randomized per cohort (6 active, 2 placebo). A total of approximately 24 to 40 subjects will be enrolled in the study with 24 subjects in Part A and up to 16 in Part B.

Part A

Subjects assigned to Part A will receive one of the following regimens:

Cohort 1 – 3 SC doses of [REDACTED] mg at [REDACTED],

Cohort 2 – 3 SC doses of [REDACTED] mg at [REDACTED], and

Cohort 3 – 2 SC doses of [REDACTED] mg at [REDACTED].

Part B

Part B will consist of up to 2 treatment cohorts. The dose and dosing intervals to be administered to subjects enrolled in these cohorts will be determined by the Sponsor based upon the available unblinded safety, PK, and PD data acquired in Part A. The decision regarding doses and dosing intervals for subjects enrolled in Part B will be made while Part A is still ongoing to allow Cohort 4 in Part B to begin without delay.

Safety Review Committee (SRC) meetings will be convened before administration of the third dose in Cohorts 1 and 2 and before the third dose in Cohorts 4 and/or 5 if a [REDACTED] regimen is selected for those cohorts. Details regarding the SRC and their responsibilities are provided in Section 5.8.

3.1.2 Study Design: Periods

The study will include 4 periods: Pre-screening, Screening, Dosing, and Observation.

Pre-screening

Sites may opt to utilize a Pre-screening Informed Consent Form (ICF) to enable performance of a complete blood count (for the absolute eosinophil numbers) in consenting subjects while each subject considers consent for the full study. Pre-screening may occur within 90 days of Visit 1.

Screening Period

During the Screening Period (Day -21 to Day -1), subjects who have given written informed consent will be assigned a subject number, undergo Screening assessments which include, among other procedures, safety assessments. Eligible subjects will be allocated to cohorts and then be randomly allocated to treatment with UPB-101 or placebo in a 3:1 ratio, respectively.

On the afternoon before the first dosing (Day -1), subjects will be admitted to the site for review of their Day -5 assessments and final Screening procedures. Subjects who continue to meet the study enrolment criteria will continue to the Day 1 Visit.

Dosing Period

On Day 1, the first day of the Dosing Period, subjects will remain housed at the site and will undergo baseline safety, PD, PK and antigenicity assessments. Following completion of those procedures, subjects who remain eligible for enrolment will be randomized and administered the first dose of the study drug. Dosed subjects will remain at the site for a minimum of 4 hours post-dose to assure subject safety. Study drug will be administered SC as outlined in Table 12.

During the Dosing Period subjects will undergo frequent safety, PD, PK and antigenicity monitoring as well as study drug dosing according to the schedule listed in Table 4 through Table 9.

Subjects will be re-admitted to the sites the afternoon before each dosing to better assure attendance, study rule compliance, and adherence to the dosing day timelines. Several procedures will be performed upon admission. Food and exercise restrictions begin the evening after admission in advance of the assessments planned for the following day. The following morning between 6 AM and 10 AM, prior to dosing, subjects will undergo safety, PD, PK and antigenicity assessments. Once these procedures have been completed, subjects will receive their assigned study drug dose. Dosed subjects will remain at the site for a minimum of 4 hours post-dose to assure subject safety.

Observation Period

The Observation Period begins after each subject has received their final study drug administration. During this period subjects will undergo periodic safety, PD, PK and antigenicity monitoring according to the schedule listed in Table 6 through Table 8. Subjects enrolled in cohorts with [REDACTED] dosing intervals will be observed for 6 months while subjects enrolled in cohorts with [REDACTED] dosing intervals will be observed for 5 months. Subjects enrolled in cohort 4 (and receiving [REDACTED] dose) will be observed for 8 months.

Upon completion of the study, subjects will undergo a Final Visit. At that visit subjects will undergo final safety, PD, PK and antigenicity monitoring according to the schedule listed in Table 6 through Table 8. In addition to the usual safety assessments, all subjects will undergo a second complete physical examination and all females of childbearing potential will undergo beta human chorionic gonadotropin serum (β -HCG) pregnancy tests.

Subjects who withdraw their consent before they have completed all study visits and subjects who have completed all their planned study visits will be asked to attend their Final Visit at which time final safety and efficacy data will be collected.

All Study Periods

All PD and PK assessments (with the exception of spirometry) will be conducted between 6 AM and 10 AM to minimize the impact of diurnal variations on biomarker assessments.

[figure not shown]
